Case report forms are developed from adaptations of NIH and industry-funded clinical trial protocols in PTSD. Study data will be recorded on paper forms and translated to a digital format without specific patient identifying information. Patient identifiers will be maintained in a separate code book that will be kept in a locked cabinet in the Principal Investigator's office at each site. These data will be preserved on site with periodic monitoring by the primary site. At the end of the study, the databases for the different sites will be merged. Data will be entered sequentially and within a timely manner so that any queries for missing information can be resolved.

B. General Statistical Considerations

Possible risk factors/confounders: We expect the randomization procedure to equalize risk factors across treatment groups; however, we will produce summary statistics to explore any unexpected differences in the values of covariates in the treatment groups. While we do not expect differences in covariates in the treatment groups, it is very likely that the response groups will be different on some relevant clinical variables (e.g., comorbid conditions). However, these should affect only the analyses that include treatment response, and not analyses such as group-related change in CAPS. Thus, we will formally assess response group differences in possible covariates of interest and incorporate any covariates identified that are considered both statistically and clinically relevant as additional main effects for the response-based analyses. Specific types of interaction effects, such as effect modifiers specified a priori, will be the subject of exploratory analysis.

Site effects: Our assumption for the analysis plan and power calculations is that the protocols will be implemented sufficiently comparatively to avoid significant site effects in the results. Given that the randomization will be blocked by site, there is no reason to believe that the

subjects will have a different a priori probability of response or will be significantly different from a clinical perspective. However, we will test for site differences in all outcome measures with appropriate univariate comparisons to ensure that this is not a significant confounder. If there is evidence of significant site differences in response, we will proceed with stratified analyses in place of the proposed analyses.

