Missing data: For those subjects randomized who do not complete treatment, an intent-to-treat approach will be implemented using linear and categorical mixed model methods. More specifically, all participants who are randomized to treatment group and have baseline measures will be included in the analysis. If the probability of a missing observation depends on either observed covariates in the model or the previous observations of the outcome variable (e.g. CAPS), these models will provide the correct conclusions (Little & Rubin, 2002). Any other missing data would be the result of incomplete recording of information or refusal of a subject to give information. Thus, the assumption that missing data are in fact missing at random (MAR), or that other variables under consideration will contain enough information to effectively model the outcome of interest, will be reasonable for these analyses.

Therefore, in the case of missing predictor variables, simple or multiple imputation methods (Little and Rubin, 2002) will be sufficient to provide “fill-in” methods so we can perform analyses of the full data set. All analyses described below will be performed on the complete data sets that result from this process. We will compare dropout patterns between groups and if there are concerns of informative dropout and/or informative intermittent missing data, we will perform sensitivity analyses to determine the effects of these assumptions on our main analyses (Molenberghs et al., 2004).

Analytic details: Continuous variables will be fit using SAS PROC MIXED, and categorical data will be fit using the gllamm add-on to Stata (Rabe-Hesketh et al; 2002). The gllamm method is preferred to SAS PROC GLIMMIX in that it is a full likelihood method which uses numerical integration for the random effects rather than a partial likelihood approximation. In addition, it provides empirical Bayes estimates of the random effects for model checking. Prior to model fitting, we will examine the distributions of the continuous outcome variables using visual inspection of histograms and boxplots to identify potential outliers. If variables are not normally distributed or contain outliers, then log transformations will be considered or appropriate nonparametric procedures will be substituted for the analyses stated.

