Multiple outcome measures: To address the possible increase in Type I errors due to multiple outcome variables, we have a priori selected a single outcome measure (CAPS total) which will maintain the significance level (α) 0.05 for the primary analysis. For secondary outcome measures, we will adjust p-values by controlling for the false discovery rate (Benjamini & Hochberg, 1995) and report both unadjusted and adjusted p-values.

Random effects: Given that the majority of outcomes are behavioral in nature, we expect that there will be significant individual level variance that will need to be incorporated into the model. Thus our overall analysis approach will be to use linear 2-level mixed models or generalized linear mixed models, as appropriate, to analyze the repeated measures data with at least a random intercept to incorporate individual level variation. We will also incorporate a random slope if necessary however, it is not always necessary in our experience, particularly with scales with a limited range such as MADRS.

VIII. HUMAN SUBJECTS

Updated January 22, 2019

A. Subject Recruitment

Men and women between the ages of 18-65 with a primary diagnosis of PTSD using the DSM-V criteria will be eligible for the study. A total of 60 subjects will be randomized (30 to Vortioxetine and 30 to placebo). These subjects will be enrolled at 2 sites, Emory University School of Medicine and Miami Miller School of Medicine. Subjects will enter this study having been recruited through referrals from outpatient clinics, or referrals from other community clinics and community clinicians (psychiatrists, psychologists, and social workers) in the greater Atlanta and Miami regions. In addition, we will advertise locally in newspapers and radio and will post recruitment messages on internet sites.

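### The primary CAPS-5 analysis can be replaced after a look at the outcomes: loosely worded distribution and site rules override the mixed model, and site, the blocking factor, is in no stated model

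*Combined protocol and SAP*

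**What the plan says.** Specific Aim 1 (Section II) judges efficacy by mean change in CAPS-5 over 12 weeks. Section VII.B then sets out the analysis.

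- **Multiple outcome measures** fixes CAPS total as the single primary outcome, at an alpha of .05.
- **Random effects** chooses two-level mixed models "to analyze the repeated measures data with at least a random intercept to incorporate individual level variation", with a random slope if needed. It lists no fixed effects.
- **Missing data** relies on these models being correct when the chance of a missing value "depends on either observed covariates in the model or the previous observations of the outcome variable".
- **Analytic details**, distribution rule: "Prior to model fitting, we will examine the distributions of the continuous outcome variables using visual inspection of histograms and boxplots". If variables look non-normal or contain outliers, "log transformations will be considered or appropriate nonparametric procedures will be substituted for the analyses stated".
- **Site effects** starts from the design, "Given that the randomization will be blocked by site", and expects no site differences. It nevertheless tests every outcome for them, "to ensure that this is not a significant confounder", and continues: "If there is evidence of significant site differences in response, we will proceed with stratified analyses in place of the proposed analyses".

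Appendix B gives the CAPS-5 total a range of 0 to 80.

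**The concern.** The plan fixes the primary outcome and its alpha, but not the analysis. Two rules that depend on the outcome data can displace the mixed model, and CAPS-5 total is not exempt from either.

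The distribution rule looks at the wrong quantity. A mixed model needs well-behaved residuals, not normal raw outcomes. The rule gives no criterion, no log constant and no named nonparametric test. A log or rank analysis would not estimate the mean change in Aim 1. A standard rank test would also lose the missing-data argument on which the plan relies.

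The site rule handles the blocking factor through a pretest instead of a model term. The plan states neither the test, its level and its time point, nor what stratified means. It is also unclear whether response means responder status or outcome in general.

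At stake is whether the reported primary result answers Aim 1, and whether a reader can tell that the analysis was chosen independently of the data.

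**Working it through.** **Inputs from the documents.** 60 patients, 30 per arm, 1:1, two sites, randomization blocked by site; d = .70 at p < .05 with stated power .80 (Section V.B); CAPS-5 range 0-80 (Appendix B).

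**Assumptions.** Two-sided testing (the plan does not say); 15 per arm per site; site pretest at .05; site shifts as listed, in the analysed outcome; 1.5 x IQR as the meaning of a boxplot outlier.

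**1. The plan's own power figure.** Normal approximation: Φ(.70 × √(30/2) − 1.96) = Φ(2.711 − 1.960) = Φ(.751) = .774. Noncentral t on 58 df: .760. The stated .80 is not reproduced. That is a separate matter; .76 is the reference below. With site in the model (57 df) and no site difference, power is still .760.

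**2. How easily the distribution rule fires.** For a normal variable the upper fence is at .6745 + 1.5 × 1.349 = 2.698 SD, and .00698 of values fall outside the two fences. With known quartiles, the chance of at least one flag in 60 values is 1 − (1 − .00698)^60 = .343. Estimating the quartiles raises this: simulations give 36-44%, depending on the quartile definition. At 2 x IQR the figure is 9-12%, and at 3 x IQR under 1%. An unstated convention therefore moves the trigger from under 1% to 44% on data with nothing wrong.

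**3. What the replacement estimates.** Take two illustrative groups with baseline 40.
- Week-12 scores 2 and 42: mean 22, change −18.
- Week-12 scores 20 and 20: mean 20, change −20.

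The mean favours the second group. On log(score + 1), the back-transformed means are √(3 × 43) − 1 = 10.4 and √(21 × 21) − 1 = 20, which favours the first. Without an added constant, the log is undefined at a total of 0. A two-sample rank test needs one value per patient, so missing visits are handled outside the likelihood and the plan's argument for data missing at random no longer applies.

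**4. Error rates of the distribution rule as written.** The check precedes model fitting and involves no treatment comparison. Switching on a pooled 1.5 x IQR flag gave type I error of .047-.052 over five assumed distributions. Power at d = .70 without dropout:

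| Data | t test | Rank test |
|---|---|---|
| Normal | .75-.76 | .73 |
| Heavy-tailed or skewed | .76-.81 | .83-.94 |

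**5. Site rule, combined within-site estimate.** Simulated type I error is .046-.050 and power about .76, whatever the site shift.

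**6. Site rule, separate site tests.** With 15 per arm, power per site is .457, so both sites succeed with probability .457² = .209. Under the null, at least one site is significant with probability 1 − .95² = .0975. The pretest fires in about 47% and 97% of null trials at shifts of 0.5 and 1.0 SD, and in about 43% and 96% when d = .70. Weighting the two branches gives:

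- Either site counts, type I error: .53 × .05 + .47 × .0975 = .072 at 0.5 SD; .03 × .05 + .97 × .0975 = .096 at 1.0 SD.
- Both must be significant, power: .57 × .76 + .43 × .209 = .523 at 0.5 SD; .04 × .76 + .96 × .209 = .231 at 1.0 SD.

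Direct simulation agrees:

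| Site shift (SD) | Type I error, either site | Power, both sites |
|---|---|---|
| 0 | .053 | .74 |
| 0.5 | .071-.073 | .52 |
| 0.8 | .090-.091 | .30 |
| 1.0 | .093-.097 | .23 |

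**The case against.** The best defence is that both rules are benign when read sensibly. The site passage speaks of confounding, which points to one combined within-site estimate, and that reading costs nothing. A constant site difference in level also cancels in change scores and is largely absorbed by the random intercept, so the step 6 figures need a site shift in the analysed outcome itself. The distribution check is made before fitting and keeps type I error near .05. Logs are only to be considered, and where the data really are non-normal a rank test may gain power. All of this stands.

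It does not supply the missing definitions. The separate-site reading remains open, and nonparametric substitution is stated as something that will happen. Nor does it answer the change of target: a gain in power for a different quantity is not a gain for Aim 1.

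The section also refers to proposed and stated analyses as if fuller model descriptions existed. The documents contain none, so the absence of site and of other fixed effects can be asserted only for the models they state.

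**Conclusion.** The point holds as a defect of specification that should be corrected; it does not invalidate the trial. A look at the outcomes, without a criterion, can move the primary analysis off mean CAPS-5 change and off the likelihood-based missing-data handling. The site rule is harmless or damaging depending on one undefined word. The sizes rest on the equal site split, pretest level, shifts and outlier rule assumed above.

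Four stronger readings are tempting but not supported:

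- **Inflated type I error from the distribution rule.** Picking the best of raw, log and rank tests would give .066-.078, but that is an upper bound for a free choice. The plan describes no choice made on treatment results.
- **A general loss of power from rank tests.** The loss is small with normal data and becomes a gain with heavy-tailed or skewed data when there is no dropout.
- **Harm from a completer analysis.** The plan proposes none. Its intent-to-treat statement covers all randomized patients with baseline measures, although it is tied to the mixed models.
- **Power lost by never including site.** At a 0.8 SD shift a model without site has type I error .034 and power .71. But the plan's own pretest, at the assumed .05 level, would fire in about 84-86% of such trials, so this is not the plan as written.

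**What to change.** - Make the primary analysis the PROC MIXED model on untransformed CAPS-5, with treatment, visit, treatment-by-visit and site as fixed effects, whatever the raw-outcome plots show. Base diagnostics on model residuals.
- Delete the site pretest and its replacement rule for the continuous outcomes, and report site-by-treatment as exploratory. If a stratified analysis is kept, define it as one combined within-site estimate.
- Report log-scale or rank-based analyses of CAPS-5 only as named sensitivity analyses, stating the log constant and the missing-data handling.
- Decide separately on site in the responder model. There, adding site makes the odds ratio conditional on site, so the choice should be stated.

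The cost is SAP wording and one degree of freedom in the linear models, with power .76 with or without site when sites do not differ. These changes do not settle the primary contrast, the handling of baseline or the optional random slope, each of which needs its own sentence.

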***See specific criterion for effective birth control methods.**

Exclusion:

CRITERION	METHOD OF ASCERTAINMENT
1. Lifetime or current diagnosis of schizophrenia or other psychotic disorder, dementia, bipolar disorder.	MINI and Clinical Evaluation
2. Subject is currently participating in another clinical trial in which s/he is or will be exposed to an investigational or non-investigational drug or	Clinical Interview

Updated **January 22, 2019**

device, or has done so within the preceding month.	
3. Subject has a prior unsuccessful trial of Vortioxetine at 20 mg/day or higher for 8 weeks or more	History
4. Current evidence or history of significant unstable medical illness or organic brain impairment, including stroke, CNS tumor, demyelinating disease, cardiac, pulmonary, gastrointestinal, renal or hepatic impairment that would likely interfere with the action, absorption, distribution, metabolism, or excretion of Vortioxetine. History of moderate or more severe TBI will also be exclusionary.	Medical chart review, clinical interview, physical exam, and laboratory testing
5. Patients who in the investigator's judgment pose a current suicidal or homicidal risk	Clinical Interview
6. DSM-5 substance abuse or dependence within the past 90 days. Subject has a positive urine toxicology test for illegal substances.	History, Urine Toxicology
7. Diagnosis of anorexia nervosa or bulimia in the past year.	MINI, History
8. Subject has a documented history of hepatobiliary disease including a history of, or positive laboratory results for hepatitis (hepatitis B surface antigen and/or hepatitis C antibody), AND clinically significant hepatic enzyme elevation, including any one of the following enzymes greater than 3 times the upper limit of normal (ULN) value (ALT, AST, ALP), or total bilirubin > 1.5 x ULN, unless consistent with presumed or diagnosed Gilbert's disease	History, Laboratory testing
9. Subject has taken systemic corticosteroids within 2 weeks of the Randomization Visit	History
10. Treatment with any other psychoactive medication within 2 weeks of Visit 1, including all antidepressants, psychoactive herbal or nutritional treatment (St Johns Wort, SAM-e), lithium, other mood stabilizers, oral antipsychotics, depot antipsychotics within 12 weeks, beta blockers, thioridazine, pimozide, opiates, anxiolytics, and sedatives (with the exception of zolpidem, eszopiclone, zaleplon, and diphenhydramine). Also any treatment with any medication that the PI judges not acceptable for this study.	History
11. Pregnancy or lactation*	Pregnancy test, assessment
12. Subjects who, in the opinion of the investigator, would be noncompliant with the visit schedule or study procedures (e.g. illiteracy, planned vacations, or planned hospitalizations during the study).	Interview/History

13. Any laboratory abnormality that in the investigator's judgment is considered to be clinically significant (blood pressure, ECG, TSH, LFT, etc.)	Laboratory testing
14. Patients who are receiving exposure-based psychotherapy that targets PTSD symptoms	Treatment History
15. Current or planned litigation or other actions related to secondary gain regarding the traumatic event	Interview
16. Subject has clinical evidence of, or EKG results indicating any of the following at either screen or Randomization Visit unless repeat EKG shows that the parameter had returned to within normal range by the Randomization Visit:  QTc > 450 msec for men, or > 475 msec for women;  Any cardiac condition or EKG evidence that the investigator feels may pose a potential safety concern.	EKG

* A serum pregnancy test is performed during the screening. Since this test might not detect the very early stage of pregnancy (i.e. maximum of 10 day period between fertilization and implantation), women of child-bearing age are excluded from the study if they do not use an effective birth control method for 15 days prior to receiving the study drug. Acceptable methods of birth control include: surgical sterility; post menopausal status (defined as no menses for at least 12 months); a double-barrier method (condoms plus diaphragm); hormonal contraceptives plus single barrier (birth control pills, implants [Norplant] or injections [Depo-Provera]), Intrauterine Device (IUD), or abstinence (no sexual activity).

E. Risks

1. General

By agreeing to participate in this study, subjects will be temporarily forgoing the opportunity to receive routine clinical care in the community. This will be clearly explained to all patients, along with the treatment strategies that are generally used in patients with PTSD. Patients will be told that standard alternative treatments exist for PTSD.

2. Screening and Evaluation

The risks and discomforts of the screening and baseline evaluations are minimal. No discomfort is expected to be associated with the physical examination or the clinical interview. Venipuncture may be associated with the momentary discomfort of the needle stick, as well as a small risk of hematoma (bruise). Subjects will be exposed to the discomfort of answering personal questions that they may find distressing.

3. Drug-free period and treatment trial

Since it is unknown whether the candidate is effective in the treatment of PTSD, participation in this trial could delay potentially effective therapy by 12 weeks. There may be a significant worsening of symptoms as the patient's medications are being discontinued, during the drug-free period or during the study itself. If the patient is discontinued from the study due to a worsening of their illness, they will be referred for standard care.

F. Procedure Specific Risks

Research interviews or study procedures will be interrupted if subjects become distressed or object to answering questions. We will not taper off medications that are clearly effective for the patient's current depression or PTSD.

Patients may withdraw at any time or be dropped from the study at the discretion of the investigator should medical contraindications to the assigned medication develop, if intolerable adverse reactions occur, if mood or anxiety worsens, or if in the clinician's judgment the patient has worsened to such a degree that further participation would put the patient at risk. If stopping criteria established by University of Miami guidelines are met, participants will be exited from the study and appropriately monitored.

In the startle testing, participants will be exposed to a Lemon Prep mild abrasive skin prepping lotion and gel for the electrodes. It is possible that subjects may experience allergic responses to the ingredients of the lotion or gels.

Risks Associated with Donation of Genetic Material

There are no physical risks associated with participation in genetic studies, apart from those routinely associated with phlebotomy, which are minimal. Psychological and social/economic risks associated with genetics studies of the kind described here are difficult to define, and remain the subject of heated controversy in the ethics community. The major risk, to the degree that any exists, is that a breach of confidentiality regarding genetic studies that resulted in third parties finding out genetic information about a person could theoretically place a person at risk for loss of insurance, loss of employment, etc. because of genotype-based discrimination. To our knowledge, no person has ever suffered harm for the reasons just described as a result of participating in a genetics research study. Regardless, our written informed consent process goes over these risks carefully. In addition, subjects have the right to "withdraw" from the research by having their DNA sample destroyed. Finally, all research records containing any subject-identifying information are stored under lock and key, or in secured computing environments. Personal identifiers are never associated directly with genotypes in the same data file—all genotype information is indexed only to de-identified subject codes. With these safeguards in place, we are confident the research is virtually without psycho-social-economic risk to subjects.

G. Protection against Risk

There are four areas in which safeguards to protect subjects from undue risk require discussion for study-related activities. These include the procedures used to obtain informed consent, procedures used to ensure confidentiality of the subjects' data, procedures used to minimize risks associated with study procedures, and risks associated with participating in the treatment study.

Informed Consent

In the consent form and discussion with an investigator, subjects are advised fully of the procedures to be used, the amount of time required of them, the possible risks and benefits of the procedures, their right to refuse participation in the study without prejudice, their right to terminate participation at any moment without prejudice, and the name and telephone number of the Principal Investigator.

Confidentiality of Subjects' Responses

In the informed consent form, subjects are told that the information they provide and all findings will be kept strictly confidential, with access limited to the research staff at the research sites and the possible exception of state or federal regulatory personnel. All data will be carefully stored in a limited access, locked room. No names will be associated with computer files or data, and no names will be associated with any published reports. Access to participant data will be limited to study staff, on an as-needed basis. Results are published as group data without the use of characteristics that would identify individual subjects. We quote information only by number in conference discussions, scientific reports, or publications, in order to maintain anonymity. Confidentiality may need to be broken in certain cases, such as when the subjects' safety is endangered.

Research Procedures

We have described above the potential risks of the research procedures and the safeguards that will be used to minimize risks. Additionally, interviewers will receive training in the importance of study information confidentiality, and in how to manage any participant distress that may be associated with responding to research questions and interviews. Subjects will be observed closely during startle testing and the procedure will be stopped immediately if a subject indicates it is too aversive. Only one subject out of approximately 600 test sessions in the [name] lab has requested that startle testing be stopped. We will terminate subjects from research participation if it is believed that such participation endangers their welfare. Any adverse events will be reported in compliance with IRB policies at Emory and Miami. If a clinically significant physical condition is identified during the course of participation, an appropriate referral to a medical treatment facility will be offered.

Study Medication

Subjects are monitored for potential reactions during the clinical trial. A physician is on call at all times between clinic visits so that adverse reactions can be evaluated and treated promptly.

H. Risk-Benefit Ratio

The potential risks detailed above are non-significant, and the investigators will make every effort to minimize their occurrence. The direct benefits from participating in this study may be decreased PTSD and depressive symptoms, but there may be no direct benefits to individual patients. Information obtained from the study will benefit society by increasing knowledge about PTSD.

I. Confidentiality of Data

All electronic records will be kept confidential to the extent permitted by law. Participants' names and other personal identifying information will be stored in electronically secured databases at the study sites. These databases are password protected and only study personnel will be given the password. Results will be published as group data without the use of characteristics that would identify individual subjects. The results of the genetic assessments will also be addressed in the same way.

J. Data and Safety Monitoring Plan

In compliance with local IRB guidelines, PIs will prepare a report annually that summarizes adverse event and protocol deviation data for the Data Safety Monitoring Board for the study. Each site will develop its own DSMB for the study.

K. Adverse Event Monitoring

Adverse events will be monitored throughout the study using the FIBSER and PRISE self-report forms, and through open-ended clinician inquiries. Monitoring will include assessment of

intensity (mild, moderate, severe) and assessment of causality (drug related, not drug related). All events will be followed to resolution or stabilization. All serious adverse events (SAE) will be collected and reported as appropriate per each site's IRB-required reporting guidelines.

A serious adverse event is one that meets any of the following criteria:

- Fatal or life threatening
- Requires or prolongs inpatient hospitalization
- Results in persistent or significant disability/incapacity
- Congenital anomaly
- Important medical event that may jeopardize the patient or require intervention to prevent a serious outcome
- Cancer

An Adverse Event is:

- any abnormal laboratory test and felt to be clinical significant
- exacerbation of chronic/intermittent pre-existing condition
- New conditions detected or diagnosed
- Signs, symptoms or clinical sequelae of a suspected interaction

The University of Miami as the lead site will establish a Data Safety Monitoring Committee (DSMC) for the duration of this study in order to oversee the safety of study participants in the study. As part of the Clinical Operations Committee, the principal investigators and sub-investigators will be having conference calls monthly and will review all data and procedures on a monthly basis. Each site PI will be ultimately responsible for monitoring the data and safety at that site and will provide continuous, close monitoring of adverse events. In addition, the investigators and study coordinators will evaluate the progress of the study, including periodic assessments of data quality and timeliness, participant recruitment, accrual and retention, participant risk versus benefit, performance of the various sites, and other factors that can affect study outcome. They will also consider factors external to the study, such as scientific or therapeutic developments that may have an impact on the safety of the participants or the ethics of the study.

L. Financial Responsibilities of Subjects

Takeda intends to supply Vortioxetine and matching placebo tablets and will finance all aspects of the study. The subjects will not bear responsibility for any costs associated with study participation.

M. Subject Compensation

Participants will receive \$40 for each post screening, in-office visit they attend, to compensate for their time and inconvenience in participating in the trial.

N. Site Monitoring

The Miami lead coordinator will be responsible for ensuring uniformity of study procedures across the two sites. The University of Miami as the lead site will establish a Data Safety Monitoring Committee (DSMC) for the duration of this study in order to oversee the safety of study participants in the study. The Committee will consist of members of the University of Miami's Department of Psychiatry and Behavioral Sciences. The committee will convene annually and will review the study activities by both study sites in a combined report. The Emory site will report their adverse events and all necessary events to the Miami site in a timely manner prior to the Miami site submitting to the Miami DSMC. Any communication, including

approval letters, from the DSMC will be distributed to the study sites and the study sponsor, as needed. The committee will also convene ad hoc as deemed necessary.

Responsibilities of a DSMC:

1. The primary responsibility of the DSMC is to review interim analyses of outcome data and to recommend whether the study needs to be changed or terminated based on these analyses.
2. The DSMC reviews interim toxicity data.
3. The DSMC reviews major modifications to the study prior to their implementation (e.g. termination, dropping an arm based on toxicity results, increasing target sample size).

IX. SOURCE OF RESEARCH MATERIALS

Blood will be collected and analyzed for the screening tests and genetic analyses. Urine samples will be collected and analyzed with a toxicology screen. We will also collect physical records in the form of questionnaires, phone screenings, and psychiatric interviews. We will request access to patient's medical records only for reasons related to patient safety. Patient charts will be kept in locked file cabinets in the offices of each study site.

Biological specimens are linked to the individual patient only through a unique research code. All documents that directly reveal the patient's identity, such as signed consent forms, are stored in charts that are marked on the outside only with the patient's code number.

